9.4.3 ANALYSIS OF THE SECONDARY ENDPOINT(S)

The primary outcome is percent weight loss, and secondary outcomes include: HbA1c levels, diabetes knowledge, dietary intake, and self-reported physical activity. All but the weight and HbA1C measures (assessed by the research coordinator) will be self-reports using established scales that have evidence of reliability (internal consistency and/or a test-retest reliability) and validity. A paired t-test will be the main analytic technique for the primary measure (percent weight loss) and all continuous outcome measures. The test of the intervention effect will be the t-test for the regression coefficient for condition, which will estimate the adjusted difference between the two conditions at posttest. That test will be two-tailed with a type I error rate of 5%. Chi-square tests will be used for all categorical outcome data. We will perform the analysis using SAS PROC GLM, Version 9.1.¹⁴⁸ We will perform these analyses in collaboration with our statistical consultant, [name].

9.4.4 SAFETY ANALYSES

N/A

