7.1 DISCONTINUATION OF STUDY INTERVENTION/EXPERIMENTAL MANIPULATION

When a subject discontinues from the intervention but not from the study, remaining study procedures will be completed as indicated by the study protocol. If a clinically significant finding is identified (including, but not limited to changes from baseline) after enrollment, the investigator or qualified designee will determine if any change in participant management is needed. Any new clinically relevant finding will be reported as an adverse event (AE). The data to be collected at the time of study intervention discontinuation will include the following: the reason(s) for discontinuing the participant from the intervention, and methods for determining the need to discontinue

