Additionally, there may be associated risks with the participant learning their A1C levels. If a participant's A1C level is in the diabetes range, they will be provided with a sheet with information on A1C levels and information about how to contact their primary care physician about their results. This sheet will provide CACOST Health Center contact information as well.

Further safety procedures consist of: (1) AE/SAE identification and follow-up; (2) monitoring for distress potentially triggered by educational content; (3) privacy/technology safeguards (e.g., wrong-number texting, shared phones). AEs are any unfavorable or unintended psychological or practical effect temporally associated with participation in the study's activities (videos, , surveys), whether or not considered related. Examples include: heightened anxiety/distress about diabetes risk, perceived breach of privacy (e.g., texts seen by others on a shared device), escalation of medical mistrust that prompts clinical concern, and elevated A1C measures that require further doctors assessments. SAEs would be rare in this context and are defined per IRB policy (e.g., death, life-threatening event, hospitalization) regardless of attribution.

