8.3.1 DEFINITION OF ADVERSE EVENTS

An AE is defined as an event that is unexpected, related or possibly related to research participation, and suggests that the research places subjects or others at a greater risk of harm than was previously known or recognized.

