8.3.3.3 EXPECTEDNESS

A member of the research team with appropriate expertise will be responsible for determining whether an adverse event (AE) is expected or unexpected. An AE will be considered unexpected if the nature, severity, or frequency of the event is not consistent with the risk information previously described for the study procedures.

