8.3.4 TIME PERIOD AND FREQUENCY FOR EVENT ASSESSMENT AND FOLLOW-UP

The occurrence of an adverse event (AE) or serious adverse event (SAE) may come to the attention of study personnel during study appointments.

All AEs, not otherwise precluded per the protocol, will be captured on the appropriate case report form (CRF). Information to be collected includes event description, time of onset, assessment of severity,

relationship to study procedures (assessed only by those with the training and authority to make a diagnosis), and time of resolution/stabilization of the event. All AEs occurring while on study will be documented appropriately regardless of relationship. All AEs will be followed to adequate resolution.

Any medical or psychiatric condition that is present at the time that the participant is screened will be considered as baseline and not reported as an AE. However, if the study participant's condition deteriorates at any time during the study, it will be recorded as an AE.

Changes in the severity of an AE will be documented to allow an assessment of the duration of the event at each level of severity to be performed. Documentation of onset and duration of each episode will be maintained for AEs characterized as intermittent.

The study coordinator will record events with start dates occurring any time after informed consent is obtained until 7 (for non-serious AEs) or 30 days (for SAEs) after the last day of study participation. At each study visit, the investigator will inquire about the occurrence of AE/SAEs since the last visit. Events will be followed for outcome information until resolution or stabilization.

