8.4.1 DEFINITION OF UNANTICIPATED PROBLEMS

This protocol uses the definition of Unanticipated Problems as defined by the Office for Human Research Protections (OHRP). OHRP considers unanticipated problems involving risks to participants or others to include, in general, any incident, experience, or outcome that meets all of the following criteria:

- Unexpected in terms of nature, severity, or frequency given (a) the research procedures that are described in the protocol-related documents, such as the Institutional Review Board (IRB)-approved research protocol and informed consent document; and (b) the characteristics of the participant population being studied;
- Related or possibly related to participation in the research (“possibly related” means there is a reasonable possibility that the incident, experience, or outcome may have been caused by the procedures involved in the research); and
- Suggests that the research places participants or others at a greater risk of harm (including physical, psychological, economic, or social harm) than was previously known or recognized.

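### Section 8.3.1 defines an adverse event by the unanticipated-problem test, against the rest of the safety rules, and Section 9.4.4 plans no summary by arm of the events collected

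*Combined protocol and SAP*

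**What the plan says.** The schedule of activities (1.3) marks AE reporting at all three appointments and during the intervention period. Section 8.3.4 has events asked about at each visit and entered on a case report form with description, onset, severity, relationship and resolution. It also requires that "All AEs occurring while on study will be documented appropriately regardless of relationship", and it records events "until 7 (for non-serious AEs) or 30 days (for SAEs) after the last day of study participation". The statistical section then has "9.4.4 SAFETY ANALYSES N/A".

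On what counts as an AE, 8.3.1 says "An AE is defined as an event that is unexpected, related or possibly related to research participation" and adds a third condition, that the event points to more risk than was already known. Section 8.4.1 lists the same three conditions for an unanticipated problem, the third being "Suggests that the research places participants or others at a greater risk of harm". Section 8.2 defines AEs differently, as "any unfavorable or unintended psychological or practical effect temporally associated with participation", whether or not they are thought to be related.

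**The concern.** There are two linked faults. The first is a stated rule that cannot be followed together with the rules around it. If 8.3.1 governs, an AE can be neither expected nor unrelated, so the later instructions to grade expectedness and relationship have nothing to act on. The protocol's own examples would be at risk. Section 8.2 names distress about diabetes risk and a raised A1C needing a doctor's assessment as AEs, yet 2.3.1 already foresees both.

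The second fault is that nothing is planned for the data once collected. Section 2.3.1 accepts some health risk from physical activity through STEPS, and 2.3.2 calls the risks minimal. The randomised comparison is the trial's own check on those statements. With N/A in 9.4.4 and more than one definition in the text, the choice of which harms to summarise, and how to count them, would be made after the data are seen.

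**Working it through.** **Step 1: the definition.** The plan gives no figure to reproduce here, so the check sets 8.3.1 beside each related rule.

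| Section | What it requires | Consistent with 8.3.1? |
|---|---|---|
| 8.4.1 | An unanticipated problem meets all three conditions | Same test, so AE and unanticipated problem become one category |
| 7.1 | Any new clinically relevant finding is reported as an AE | No: no condition on expectedness or relationship |
| 8.2 | Temporal association is enough, related or not | No |
| 8.3.2 | An SAE is defined by its outcome | Not affected; 8.2 adds that attribution does not matter |
| 8.3.3.1 | Mild, moderate, severe | No conflict |
| 8.3.3.2 | AEs graded Related or Not Related | No: the second grade would always be empty |
| 8.3.3.3 | AEs judged expected or unexpected | No: the expected class would always be empty |
| 8.3.4 | AEs documented regardless of relationship | No: the clause would have no effect |
| 8.3.5 | AEs reported whether or not related | No: as for 8.3.4 |

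So 8.3.1 is the outlier. How much it would exclude cannot be fixed from the text, because 8.3.3.3 says "An AE will be considered unexpected if the nature, severity, or frequency of the event is not consistent with the risk information". A foreseen kind of event could still qualify through unusual severity or frequency.

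Adopting 8.2 unchanged would not fully solve this. Its wording covers psychological or practical effects, and read literally it may omit a physical event such as the exercise injury discussed in 2.3.1.

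**Step 2: the analysis.** I looked for a summary by arm anywhere else in the supplied text.

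- 8.3.5, 8.3.6 and 8.4.2 cover reports of single events to oversight bodies.
- 9.4.1 to 9.4.3 cover weight, HbA1c, knowledge, diet and physical activity. Their chi-square sentence concerns categorical outcome data and does not name AEs.
- 9.4.8 declines individual listings by measure and time point.
- 10.1.6 describes weekly review by the principal investigator.
- 10.1.11 promises results submission but specifies no safety content.

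None of these is a safety summary by arm.

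**Step 3: what a table could show.** The documents give no AE rates, so the counts here are assumptions. With 164 randomised (9.2) in equal arms, n = 164/2 = 82.

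- Zero events in an arm: upper two-sided 95% limit = 1 − 0.025^(1/82) = 4.4%.
- Four participants with an event in each arm: risk difference 0, Newcombe score 95% interval −7.6 to 7.6 percentage points.

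Such a table is descriptive and could not establish that the arms are equally safe.

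**The case against.** The strongest reply is that the practical loss may be small. Section 8.3.4 is the operative recording rule and is broad, activity injuries reported to staff get a separate report under 2.3.1, and SAEs are defined by outcome. This is a low-risk behavioural trial. Its lack of blinding (6.3) limits any comparison of reported events, and the intervals will be wide. The Data and Safety Monitoring Plan (7.2) and the Manual of Procedures (10.1.10) are cited but not supplied, and either could hold a summary. Sections 4.1 and 8.2 are partly in the past tense, so changing the definition now may not change what was collected.

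Most of this stands as a limit on size. It does not remove the contradiction in 8.3.1 or make N/A the right entry in the statistical section. Low expected risk argues for a simple table, not for none.

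A reader might go further and infer that AEs have been lost. The documents do not show that staff used 8.3.1 as a filter. A reader might also try to show with assumed counts that the narrow definition would hide a real excess of injuries. That result turns on the counts chosen: at 82 per arm, 12 versus 4 gives a difference of 9.8 points (0.5 to 19.4), but 11 versus 4 gives 7/82 = 8.5 points (−0.5 to 18.0). With no event rate in the documents, neither is evidence about this trial.

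**Conclusion.** The point holds. Section 8.3.1 states the wrong test for an AE and conflicts with 7.1, 8.2, 8.3.3.2, 8.3.3.3, 8.3.4 and 8.3.5. Section 9.4.4 plans no safety analysis, and the supplied text has no summary by arm. The second statement is limited to the supplied text.

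The effect on AE counts cannot be quantified, since it depends on which definition staff used and on event rates that the documents do not give. A reader might infer that all safety data, or the trial's main conclusions, are compromised. The text does not support that: the SAE rows of a table do not depend on 8.3.1, and the primary and secondary efficacy analyses are untouched. The matter is of moderate importance and should be corrected because the remedy is cheap.

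**What to change.** 1. In 8.3.1, define an AE as any unfavourable physical, psychological or practical event on study, whether or not expected or related. Bring 8.2 into line, and keep the three-part test for unanticipated problems in 8.4.1 only. If collection is complete, state which definition staff applied.

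2. Replace N/A in 9.4.4 with a descriptive table in all randomised participants by assigned arm. It should give the number and percentage with at least one AE and with at least one SAE, recorded within the 8.3.4 window, overall, by maximum severity (8.3.3.1) and by relatedness (8.3.3.2). Include a row for physical-activity injury that takes in injuries reported to staff under 2.3.1. Give 95% intervals for the risk differences, with no hypothesis test, and label the table as resting on unblinded ascertainment.

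The cost is one corrected definition, one paragraph and one small table, built mainly from items that 8.3.4 already puts on the case report form. The intervals will be wide. Events not recorded because the narrow definition was applied may not be recoverable, although injuries reported to staff should have their separate report.

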9.4.5 BASELINE DESCRIPTIVE STATISTICS

All analyses will control for any confounding variables not managed through randomization (i.e., group difference $p < .10$).

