1.3 SCHEDULE OF ACTIVITIES

The schedule below is provided as an example and should be modified or replaced as appropriate.

Mobile Diabetes Prevention for Hispanics Living in Rural Areas
R44MD014082

Version 1
16 Jan 2026

	Pre-screening (Pre-consent)	Appointment 1 Day 1	Day 8-91	Appointment 2 Day 92	Appointment 3 Day ~175
Study information sent to potential participants	X				
Confirmatory eligibility screening	X				
Informed Consent		X			
Demographics		X			
Outcome Evaluation					
Weight measurement		X		X	X
A1C Measurement		X		X	X
Knowledge Questionnaire		X		X	X
Health Behavior Questionnaire		X		X	X
Randomization		X			
Control Intervention			X	X	
Experimental Intervention			X		
Adverse Events Reporting		X	X	X	X

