9.2 SAMPLE SIZE DETERMINATION

We examined power using treatment effects from two sources: 1) a meta-analysis examining the overall effectiveness of mobile device interventions on weight loss¹⁵⁴ and 2) a digital diabetes prevention program for low-income patients.⁸⁵ First, a meta-analysis examining the effects of mobile device interventions on weight loss found an average effect size of Cohen's d : 0.43 (95% CI:0.252-0.609; $p < 0.01$) across 11 mobile-based intervention studies.¹⁵⁴ This indicates an overall medium effect size. Second, Kim et al.⁸² developed and tested a mobile-based diabetes prevention program for a multi-racial/ethnic population. This study yielded a mean weight loss of 4.4% (SD 7.7%) at 12 months. This finding is associated with a Cohen's d =0.57, which is considered a medium effect size. To ensure our study is fully powered, we conducted our power analysis using the smaller effect size (Cohen's d =0.43) from Lyzwinski et al.¹⁵⁴, who examined the effects of mobile-based interventions on our primary outcome, participant weight loss.

We estimated power for the paired t-test for %weight loss (primary outcome). The G*Power 3.1 program¹⁵⁷ was used to determine that a Cohen's d of 0.43 and an α error probability of 0.05 requires a final sample size of 136 to be sufficiently powered ($1 - \beta$ error probability) at 0.80. Presuming a 20% attrition rate, randomizing a final sample size of 164 participants should be sufficient to detect significant differences in % weight loss across the two survey time points (i.e., at baseline and 3 months after the end of the intervention).

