9.4.2 ANALYSIS OF THE PRIMARY ENDPOINT(S)

The primary outcome is percent weight loss, and secondary outcomes include: HbA1c levels, diabetes knowledge, dietary intake, and self-reported physical activity. All but the weight and HbA1C measures (assessed by the research coordinator) will be self-reports using established scales that have evidence of reliability (internal consistency and/or a test-retest reliability) and validity. A paired t-test will be the main analytic technique for the primary measure (percent weight loss) and all continuous outcome measures. The test of the intervention effect will be the t-test for the regression coefficient for condition, which will estimate the adjusted difference between the two conditions at posttest. That test will be two-tailed with a type I error rate of 5%. Chi-square tests will be used for all categorical outcome data. We will perform the analysis using SAS PROC GLM, Version 9.1.¹⁴⁸ We will perform these analyses in collaboration with our statistical consultant, [name].

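### Covariates are chosen by a baseline p < .10 screen instead of being named in advance; fixing the baseline value of each outcome is a free improvement, mainly for the secondary outcomes

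*Combined protocol and SAP*

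**What the plan says.** Section 9.4.5 states that "All analyses will control for any confounding variables not managed through randomization", and defines such variables by a group difference at p < .10. It gives no candidate list, no cap on the number of covariates and no named test. Because it covers all analyses, it reaches the primary endpoint.

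Sections 9.4.1 to 9.4.3 describe the treatment test as the t-test on the regression coefficient for condition, "which will estimate the adjusted difference between the two conditions at posttest", two-tailed at 5%. They do not say what the difference is adjusted for. The same sections also state: "A paired t-test will be the main analytic technique for the primary measure (percent weight loss) and all continuous outcome measures". A paired t-test takes no covariates, so the default model for a baseline value that is not flagged is unclear.

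Section 8.1 lists weight, A1C, the knowledge questionnaire and the health behavior questionnaire as baseline measures taken before randomization. The schedule in Section 1.3 repeats them at all three visits (for example the row "A1C Measurement"). Section 6.3 describes permuted blocks of 4 and 6 and names no stratification factor, so no design variable is there to adjust for.

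**The concern.** If randomization is sound, baseline differences between arms are chance. A significance screen therefore picks covariates by luck, when what matters is how strongly a variable predicts the outcome. A baseline A1C or knowledge score that predicts its own follow-up value well would be guaranteed a place in the model only when it happened to be imbalanced.

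Three things are at stake: precision that the collected baseline data could supply, test size that no longer matches the stated 5%, and a final model that depends on the data. The last applies to every endpoint, including the primary one.

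**Working it through.** **Inputs from the protocol.** d = 0.43, alpha 0.05, power 0.80, final N 136, 20% attrition, 164 randomized (Section 9.2); two-tailed test (Section 9.4.2); screen at p < .10 (Section 9.4.5). 164 × 0.8 = 131.2, or about 66 per arm.

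**Input not in the protocol.** The correlation r between a baseline value and its outcome is an assumption, shown over a range.

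**1. The plan's own figure.** Section 9.2 says that "an α error probability of 0.05 requires a final sample size of 136". A two-sample noncentral-t calculation gives 68 per arm = 136 only if the test is one-sided. The two-sided answer is 86 per arm = 172. At 136 evaluable, unadjusted two-sided power is about 0.70. That is a separate issue, but it means there is little power to spare.

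**2. What the screen selects.** Under randomization P(baseline p < .10) = 0.10 for any one variable, so it is left out 90% of the time whatever its prognostic value. For k independent candidates, P(at least one flagged) = 1 − 0.9^k, which is 41% for k = 5 and 65% for k = 10. The protocol does not give k. These figures show how unpredictable the model is. They do not measure harm, because adjusting for a flagged variable that predicts nothing costs only one degree of freedom.

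**3. Precision by analysis.** With unit outcome SD, SE = √(V × 2/n), n = 66 per arm:

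| Analysis | V | SE, r = 0.5 | SE, r = 0.7 |
|---|---|---|---|
| Follow-up values, unadjusted | 1 | 0.174 | 0.174 |
| Change score | 2(1 − r) | 0.174 | 0.135 |
| Fixed baseline covariate | 1 − r² | 0.151 | 0.124 |

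**4. Simulated operating characteristics.** 66 per arm, d = 0.43, two-sided 5%, one baseline covariate, 40,000 replicates. The rule adjusts if baseline p < .10 and otherwise uses the default shown.

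| r | Rule, follow-up default | Rule, change default | Fixed covariate | Type I error, rule with follow-up default |
|---|---|---|---|---|
| 0.5 | 0.71 | 0.71 | 0.81 | about 4.0% |
| 0.7 | 0.72 | 0.89 | 0.93 | about 3.0% |

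A larger simulation at 68 per arm (200,000 null and 100,000 alternative runs per r) agrees: 0.72 against 0.82 at r = 0.5 and 0.74 against 0.93 at r = 0.7, with type I error 4.1% and 3.0% under the rule. Fixed adjustment stays at about 5% throughout.

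**5. Why the error is conservative.** In trials that are not flagged, the baseline difference is known to be small, so the unadjusted difference varies less than its standard error assumes. At 68 per arm, type I error among those trials is 4.0% at r = 0.5 and 2.8% at r = 0.7. Among flagged trials the adjusted test is close to 5% (5.0% and 4.8%).

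**6. The primary endpoint.** Percent weight loss already uses baseline weight, so its correlation with baseline weight may be small. At 68 per arm, the rule gives 0.70 against 0.70 fixed at r = 0, and 0.71 against 0.74 at r = 0.3. Type I error under the rule is 5.0% and 4.6%. The loss is at most about 3 points.

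**The case against.** The strongest reply is that the regression wording may already mean analysis of covariance on the pretest, with Section 9.4.5 only adding further covariates. On that reading the precision loss disappears. The paired t-test wording could instead point to change scores. At r = 0.7 that default leaves a loss of about 3 points (type I error 4.3%), though at r = 0.5 it does no better than follow-up values, and at lower r it does worse. This stands in part: a reader might infer that raw follow-up values are what the plan compares whenever nothing is flagged, but the documents do not say so. It does not rescue the rule, because no adjuster is named and Section 9.4.5 remains the only stated criterion.

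A reader might also infer that the rule inflates false positives. It does not; in every setting examined the type I error is at or below 5%, apart from simulation error. Nor do the documents support a loss of some 20 points on the primary endpoint. That figure pairs the primary outcome's effect size with a correlation of 0.7, which is an assumption more plausible for the secondary measures. The documents give no correlation for any outcome and no effect size for the secondary ones.

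Finally, Sections 2.3.1 and 9.3 let participants decline weight or A1C, so a fixed baseline covariate needs a rule for missing values. That is correct, and the fix covers it.

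**Conclusion.** The concern holds in limited form. The rule is in the plan, and it makes the model depend on chance imbalance for every endpoint; that conclusion needs no assumption beyond valid randomization.

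The size is less certain. If follow-up values are the default, the cost on A1C, knowledge, eating pattern and physical activity is about 10 power points at r = 0.5 and about 20 at r = 0.7. Those correlations are assumed, and d = 0.43 is borrowed from the primary outcome. With a change-score default the loss at r = 0.7 falls to about 3 points, and if the pretest is always in the model there is none. For percent weight loss the loss is small, at most about 3 points for r up to 0.3. At no correlation examined does the screen do materially better than a fixed covariate. This is a free improvement, not an error that threatens the validity of the primary result.

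**What to change.** - Delete the p < .10 rule from Section 9.4.5 and present baseline tables descriptively.
- In Sections 9.4.1 to 9.4.3, replace the mixed paired-t and regression wording with one model: each continuous outcome is regressed on condition, with the pre-randomization value of that outcome as a fixed covariate.
- Use baseline weight for percent weight loss.
- For physical activity use the baseline questionnaire value. Under Section 8.1 the Fitbit baseline week begins after assignment, so it is not a pre-randomization measure.
- Name any other covariates in advance, and state that missing baseline values are handled by the imputation planned in Section 9.3.
- Record the change before outcomes are examined by arm. Parts of Sections 4.1 and 8.2 are in the past tense, so the dated record should say whether any outcome data had been seen by arm.

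The cost is analysis-plan wording. No participants, visits or measurements are added.
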